## 2. Schedule of Activities

**Table ITSB.1. Schedule of Activities**

	Screen a	Lead-In		Treatment Period												Safety Follow-Up	ED b
eCRF Visit Number	1	2	3 c	4	5 c	6 c	7	8 c	9 c	10	11 c	12	13 c	14 c	15	801 d	ED
Weeks from Randomization	-5	-4	-2	0	2	4	6	8	10	12	15	18	21	24	26	28	
Visit Window (±days)		3	3	3	7	7	7	7	7	7	7	7	7	7	7	7	
Informed Consent/Assent (if applicable)	X																
IWRS	X	X	X	X	X	X	X	X	X	X	X	X	X	X	X	X	X
Patient eligibility review	X	X															
Randomization				X													
Clinical Assessments																	
Demographic data e	X																
Medical history, preexisting conditions	X																
Previous diabetes therapy	X																
Record Personal CGM/FGM use (yes/no)				X													
Height f	X			X						X					X		X
Weight	X	X		X			X			X		X			X		X
Vital signs (sitting SBP, DBP, and HR) g	X	X		X			X			X		X			X		X
Concomitant medications	X	X	X	X	X	X	X	X	X	X	X	X	X	X	X	X	X
Adverse events and product complaints		X	X	X	X	X	X	X	X	X	X	X	X	X	X	X	X
Focused physical exam (including skin evaluation) h	X	X		X			X			X		X			X		X
Basal insulin dose assessment i		X	X	X	X	X	X	X	X	X	X	X	X	X	X		X
Basal insulin dose titration j		X	X	X	X	X	X	X	X	X							

	Screen a	Lead-In		Treatment Period												Safety Follow-Up	ED b
eCRF Visit Number	1	2	3 c	4	5 c	6 c	7	8 c	9 c	10	11 c	12	13 c	14 c	15	801 d	ED
Weeks from Randomization	-5	-4	-2	0	2	4	6	8	10	12	15	18	21	24	26	28	
Visit Window (±days)		3	3	3	7	7	7	7	7	7	7	7	7	7	7	7	
Prandial insulin dose assessment		X	X	X	X	X	X	X	X	X	X	X	X	X	X		X
Prandial insulin dose titration l				X	X	X	X	X	X	X							
Ancillary Supplies/Diaries/IP																	
Dispense blood glucose meter and ancillary supplies and complete training k,l		X		X			X			X		X					
Diabetes education and nutrition counseling l		X															
Dispense study diaries and complete training l		X		X			X			X		X					
Collect study diaries				X			X			X		X			X		X
Dispense IP		X		X			X			X		X					
Train on collecting 4- and 7-point SMBG profiles m		X															
Remind patient of 7-point SMBG requirements			X						X					X			

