Unless otherwise noted, all tests of treatment effects will be conducted at a 2-sided alpha level of 0.05, and CIs will be calculated at 95%, 2-sided. All tests of interactions between treatment groups and other factors will be conducted at a 2-sided alpha level of 0.10. Countries in similar geographic regions with fewer than 10 patients, based on all randomized population, will be pooled to achieve a pooled country of at least 10 patients. All analyses using country in the model will use a pooled country, unless otherwise specified. The final pooling by country and geographic region will be finalized prior to data lock.

Baseline is defined as the last non-missing measurement at or before the randomization visit (Visit 4), unless otherwise specified.

A restricted maximum likelihood-based, mixed-effect model repeated-measure (MMRM) analysis will be used to analyze continuous longitudinal variables. All the longitudinal observations at each scheduled postbaseline visit will be included in the analysis. The model for

the analysis of the primary efficacy endpoint of change from baseline in HbA1c will include the fixed class effects of treatment, strata (pooled country, type of basal insulin, and age group), visit, and treatment-by-visit interaction, as well as the continuous, fixed covariate of baseline value. For analyses of variables other than HbA1c, the HbA1c stratum ( $\leq 8.0\%$ ,  $> 8.0\%$ ) will be included in the model. An unstructured covariance structure will be used to model the within-patient errors. Significance tests will be based on least-squares (LS) means and Type III tests. SAS PROC MIXED will be used to perform the analysis. If this analysis fails to converge, the following covariance structures will be tested, in order:

- Toeplitz with heterogeneity
- Autoregressive with heterogeneity
- Compound symmetry with heterogeneous variances
- Toeplitz
- Autoregressive
- Compound symmetry without heterogeneous variances.

The first covariance structure that converges will be used. The Kenward-Roger approximation will be used to estimate denominator degrees of freedom.

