Continuous safety variables, as well as the change from baseline for these variables, will be analyzed by MMRM or ANCOVA models. For categorical variables, Fisher's exact test or Pearson's chi-square test will be used to compare treatment groups, unless otherwise specified.

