CGM outcomes	All Randomized Patients with at least one from baseline and post-baseline observations	Visit 4	Visit 15
Basal, bolus, and total insulin doses, and bolus/total insulin dose ratios continuous analysis	All Randomized Patients	Last of Visits 3-4	Visits 5-15 prior to discontinuation of IP

Baseline and Postbaseline Definitions and Patient Population by Study Period and Type of Analysis

Study Period/Analysis	Patient Population	Baseline Observations	Post-Baseline Observations
7-point SMBG	All Randomized Patients with a baseline and at least one post-baseline observation	Visit 4 prior to initiation of IP	Visits 10 and 15 prior to discontinuation of IP
Health outcomes (PedsQL)	All Randomized Patients with a baseline and a post-baseline observation	Visit 4	Visits 15 prior to discontinuation of IP
Safety Laboratory Tests (chemistry, hematology) – continuous analysis	All Patients in the Safety Population with a baseline and a post-baseline observation	Last of Visits 1-4	Last of Visits 5-15 (planned including early discontinuation visits) regardless of IP use
Safety Laboratory Tests (chemistry, hematology) – categorical analysis	All Patients in the Safety Population with a normal baseline (with respect to the direction being analyzed) and a post-baseline observation	Last of Visits 1-4	Visits 5-15 (including unplanned visits) regardless of IP use
Hypoglycemia events	Safety Population	All Visits 2-4	All Visits 5-15 prior to discontinuation of IP
Weight and vital signs	All Patients in the Safety Population with a baseline and a post-baseline observation	Last of Visits 1-4	Visits 7, 10, 12, 15 prior to discontinuation of IP
Anti-insulin lispro antibodies	Safety Population	Visit 4	Visits 7, 10, 15 regardless of IP use
TEAE	Safety Population	Prior to first dose of randomized IP (or v4 date if missing), after first dose of open label Humalog (or v2 date if missing)	From randomization to Week 26 prior to discontinuation of IP OR from randomization to safety follow-up

Abbreviations: ANCOVA = analysis of covariance; HbA1c = hemoglobin A1c; IP = investigational product; ITT = intention-to-treat; MMRM = mixed-effect repeated measures model; PedsQL = Pediatric Quality-of-Life; SMBG = self-monitored blood glucose; TEAE = treatment-emergent adverse event.

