5.12.6. Vital Signs and Other Physical Findings

Postbaseline measurements and change from baseline to post-baseline for vital signs and physical characteristics (systolic blood pressure, diastolic blood pressure, pulse rate, height, weight, BMI) at the scheduled visits will be summarized for patients who have both baseline and at least 1 postbaseline result.

The measurements during the treatment period (0 to 26 weeks) will be analyzed by an MMRM model with treatment, baseline value of the response variable, visit, and visit by treatment interaction as fixed factors and patient as the random factor.

An ANCOVA model will also be used for the analysis of the last nonmissing observation (planned measurements including early discontinuation) during the treatment period. The ANCOVA models are the same as those used for clinical laboratory measures.

The percentages of patients with treatment-emergent high or low vital signs at any time during the treatment period (0 to 26 weeks) will be summarized by treatment group for patients who have both baseline and at least 1 postbaseline measurement. A treatment-emergent high result is defined as a change from a value not meeting criteria for the high limit during the baseline period to a value meeting the criteria for the high limit at any time that meets the specified change amount during the treatment period. A treatment-emergent low result is defined as a change from a value not meeting criteria for the low limit during the baseline period to a value meeting the criteria for the low limit at any time that meets the specified change amount during the treatment period. Treatment comparison will be based on Fisher's exact test. [Table ITSB.5.5](#) will be used to define the low and high limits and change thresholds.

Table ITSB.5.5. Categorical Criteria for Abnormal Treatment-Emergent Blood Pressure and Pulse Measurement for Children and Adolescents

Age (years)		Systolic BP, mm Hg (Supine or sitting – forearm at heart level)	Diastolic BP, mm Hg (Supine or sitting – forearm at heart level)	Pulse/HR, bpm (Supine or sitting)
Infant <2	Low	≤70 and decrease ≥15	≤35 and decrease ≥10	<70 and decrease ≥25
	High	≥112 and increase ≥15	≥74 and increase ≥10	>190 and increase ≥25
Child 2-4	Low	≤75 and decrease ≥15	≤40 and decrease ≥10	<60 and decrease ≥25
	High	≥116 and increase ≥15	≥76 and increase ≥10	>160 and increase ≥25
Child 5-9	Low	≤80 and decrease ≥15	≤45 and decrease ≥10	<60 and decrease ≥25

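### SAP 5.12.6 makes patient a random factor and names no within-patient covariance; read literally, this departs from the protocol's unstructured rule and can understate the Week 26 standard error for weight change

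*SAP*

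**What the plan says.** Protocol 10.3.1 lays down a general rule. A restricted maximum likelihood "mixed-effect model repeated-measure (MMRM) analysis will be used to analyze continuous longitudinal variables". On covariance it says: "An unstructured covariance structure will be used to model the within-patient errors". An ordered list of fallback structures and Kenward-Roger degrees of freedom follow. Protocol 10.3.4 adds: "Continuous safety variables, as well as the change from baseline for these variables, will be analyzed by MMRM or ANCOVA models".

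The SAP restates the unstructured rule, the fallbacks and Kenward-Roger in Section 5.11.1, inside the HbA1c model. The insulin-dose and SMBG models (5.11.5) and the glucose-variability models (5.11.7) inherit it, because each is described as similar to the primary-outcome model.

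SAP 5.12.6 has no such link. It writes out its own MMRM for blood pressure, pulse, height, weight and BMI, with treatment, baseline, "visit, and visit by treatment interaction as fixed factors and patient as the random factor". No covariance structure is named. SAP 5.12.7.1 uses the same wording for antibody level. SAP 5.12.6 then adds a second analysis: "An ANCOVA model will also be used for the analysis of the last nonmissing observation (planned measurements including early discontinuation) during the treatment period".

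For weight and vital signs, SAP Table ITSB.5.2 gives the post-baseline observations as "Visits 7, 10, 12, 15 prior to discontinuation of IP". In the Schedule of Activities, the row "Weeks from Randomization" places these visits at Weeks 6, 12, 18 and 26. Height is scheduled after baseline only at Weeks 12 and 26, apart from early-discontinuation visits.

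**The concern.** A random patient effect with no residual structure gives every visit the same variance and every pair of visits the same correlation. The patients are aged 1 to <18 years. Children gain weight at different rates, so change from baseline can be expected to spread out with time and to vary more at Week 26 than at Week 6. A single pooled variance would then be too small for Week 26, the visit named in exploratory Objective 10 (weight change). The 95% interval at that visit would be too narrow and the p-value too small. SAP 5.1 requires intervals and p-values to be displayed for continuous measures, and in a pediatric trial these are growth comparisons that readers will look at.

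**Working it through.** **Plan's own figures.** The documents give no SD, power or error rate for weight, height or BMI. The only target is nominal: "all tests of treatment effects will be conducted at a 2-sided alpha level of 0.05". The arm sizes used in the simulation below reproduce from Protocol 10.1: 240/0.85 = 282.4, so 283; 120/0.85 = 141.2, so 142; 283 + 283 + 142 = 708. Arm size cancels from the standard-error ratio.

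**Assumptions (not from the documents).** Change in weight is a child-specific linear growth deviation with SD s (kg per 26 weeks), plus independent measurement error with SD m at baseline and at each visit. Then

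Var(t) = (s·t/26)² + 2m².

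**Formula.** With complete, balanced data, a random-intercept model gives each visit the mean of the visit variances. So

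R = SE(random intercept)/SE(correct) at Week 26 = √[mean Var(t) / Var(26)],

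type I error = 2·(1 − Φ(1.96·R)).

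**Weight, Weeks 6, 12, 18, 26.** (t/26)² = 0.053, 0.213, 0.479, 1.000; mean 0.436.

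| s (kg) | m (kg) | Var(26) | Mean variance | R | Type I error |
|---|---|---|---|---|---|
| 2.5 | 0.5 | 6.25 + 0.50 = 6.75 | 3.227 | 0.69 | 17.5% |
| 2.0 | 0.5 | 4.00 + 0.50 = 4.50 | 2.246 | 0.71 | 16.6% |
| 2.5 | 0.8 | 6.25 + 1.28 = 7.53 | 4.007 | 0.73 | 15.3% |
| 1.0 | 0.5 | 1.00 + 0.50 = 1.50 | 0.936 | 0.79 | 12.2% |
| 1.0 | 0.8 | 1.00 + 1.28 = 2.28 | 1.716 | 0.87 | 8.9% |
| 1.0 | 1.0 | 1.00 + 2.00 = 3.00 | 2.436 | 0.90 | 7.7% |
| 0 | any | 2m² | 2m² | 1.00 | 5.0% |

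Over s = 1.0 to 2.5 and m = 0.5 to 0.8, R is 0.69 to 0.87 and the type I error about 9% to 18%.

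**Other shapes of variance growth for weight.** If half of the Week 26 variance comes from growth, the error is 9.7% with linear slopes and 8.0% with a random walk. If all of it does, it is 19.5% and 13.0%. If the SD rises linearly and is only 1.1 or 1.2 times as large at Week 26 as at Week 6, it is 6.2% or 7.3%.

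**Height, Weeks 12 and 26.** The mean of (t/26)² is (0.213 + 1)/2 = 0.607. If half to all of the Week 26 variance comes from growth, the error is 7.9% to 12.7% with linear slopes and 6.8% to 9.4% with a random walk, so about 7% to 13%.

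**Simulation.** 2000 runs per case, arms 283/283/142, 15% dropout, no treatment effect, LY900014 against Humalog at Week 26. The Monte Carlo standard error at 5% is √(0.05·0.95/2000) = 0.5 percentage points. The comparator is a Week 26 ANCOVA that uses that visit's own variance.

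| Case (s, m) | Random intercept | Week 26 variance |
|---|---|---|
| Weight (2.0, 0.5) | 17.0% | 4.9% |
| Weight (1.5, 1.0) | 9.7% | 5.0% |
| Height (1.5, 0.5), 2 visits | 11.4% | 4.9% |
| BMI (0.8, 0.5), 2 visits | 9.5% | 5.9% |
| BMI (0.8, 0.5), 4 visits | 11.3% | 5.4% |
| Constant variance (blood pressure or pulse) | 5.8% | 5.6% |

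In the first row the mean standard error is 0.129 kg under the random intercept and 0.193 kg with the Week 26 variance. The simulation agrees with the formula (17.0% against 16.6%).

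**The case against.** The strongest reply is that the protocol already supplies the covariance. SAP 5.12.6 does not use the words random intercept, constant variance or compound symmetry. Protocol 10.3.1 covers continuous longitudinal variables in general. Protocol 10.3.3.3 sends tertiary variables such as weight to the models of 10.3.3.1, which refers back to 10.3.1 for the covariance. SAP 5.1 says that changes to protocol methods and their justification will be described in the SAP or the study report, and the SAP revision history lists no covariance change. On this view the sentence in 5.12.6 is loose wording and nobody would fit compound symmetry.

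Much of this stands. A reader might infer that the SAP has chosen a constant-variance model and that the Week 26 intervals will be wrong. The documents do not support that as a certainty.

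The reply does not close the gap, however. Protocol 10.3.3.3 also leaves details of the tertiary analyses to the SAP, and the SAP then writes a model of its own. A random patient intercept cannot be added to an unstructured residual covariance, because the intercept variance is not separately identifiable. A programmer therefore cannot follow both texts literally. The literal SAP sentence is a random-intercept model, and no reason is given for it.

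Two further points stand in full. The size depends on assumed SDs. And the last-observation ANCOVA in the same section does not pool variance across visits, so it is free of this fault, although the SAP does not say which of the two analyses takes precedence.

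**Conclusion.** The point holds as a conflict between SAP 5.12.6 and Protocol 10.3.1, and its severity is minor. The statistical consequence rests on two conditions: that the model is programmed as a random intercept, and that the variance of change grows over 26 weeks. The second is expected for weight at these ages but is not documented. Under the assumed SDs the type I error for weight at Week 26 is about 9% to 18%. With smaller variance growth it falls towards 5%, so a general statement that the error is far above nominal would go beyond the documents.

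Height is less affected (about 7% to 13%) because it has only two scheduled post-baseline visits. Blood pressure and pulse, with roughly constant variance, are little affected. A reader might extend the argument to antibody level in SAP 5.12.7.1, which has the same wording. Differing growth rates say nothing about percent binding, and no inflation has been shown there.

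The primary and gated HbA1c tests have their own stated covariance and are not touched.

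**What to change.** In SAP 5.12.6, delete the clause that makes patient the random factor. State instead that the model uses an unstructured within-patient covariance, with the fallback sequence and Kenward-Roger degrees of freedom of SAP 5.11.1. Make the same edit in SAP 5.12.7.1, there only for consistency with the protocol.

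The cost is one sentence in each of two SAP sections and the matching line of code. Data collection, design and sample size do not change. In the simulations, using the Week 26 variance brought the type I error to between 4.9% and 5.9%, which is nominal within simulation error.

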5.12.7. Immunogenicity

Blood samples for immunogenicity testing will be collected to determine antibody production against insulin lispro for all randomized patients since Visit 1 prior to the first dose of open label Humalog used during the lead-in. Therefore, the blood sample result at Visit 1 will be considered as the anti-insulin lispro level at baseline for this study.

The assessment of immunogenicity will include analyses of treatment-emergent anti-insulin lispro antibody up to Visit 15.

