- For the 7-point self-monitored blood glucose (SMBG) profiles, the profiles measured after the first IP dose date and prior to the last IP dose date will be considered as data on IP.

Unless otherwise noted, all tests of treatment effects will be conducted at a 2-sided alpha level of 0.05, and confidence interval (CI) will be calculated at 95%, 2-sided. All tests of interactions between treatment groups and other factors will be conducted at a 2-sided alpha level of 0.05. Countries in similar geographic regions with fewer than 10 patients, based on all Randomized Population, will be pooled to achieve a pooled country of at least 10 patients. All analyses using country in the model will use a pooled country, unless otherwise specified. The final pooling by country and geographic region will be finalized prior to data lock.

[Table ITSB.5.2](#) shows the definition of baseline and post-baseline for each variable to be analyzed. The baseline variables are derived from the evaluable data during the baseline period.

Table ITSB.5.2. Baseline and Postbaseline Definitions and Patient Population by Study Period and Type of Analysis

Study Period/Analysis	Patient Population	Baseline Observations	Post-Baseline Observations
Lead-In Period			
HbA1c ANCOVA	All Randomized Patients	Visit 1	Visit 4 prior to initiation of IP
Basal, bolus, and total insulin doses, and bolus/total insulin dose ratios continuous analysis	All Randomized Patients	Not applicable	Visit 3-4
TEAE	All Enrolled Patients	Prior to first dose of open-label insulin lispro (or Visit 2 date if the dose date is missing)	The entire lead-in period after first dose of open-label insulin lispro and prior to the first dose of IP (or Visit 4 if the dose date is missing)
26-Week Treatment Period (including Safety Follow-Up Visit where applicable)			
HbA1c ANCOVA (ITT estimand)	All Randomized Patients	Last of Visits 1-4	Visit 15 with imputation for patients who discontinue study prior to Visit 15
HbA1c MMRM (efficacy estimand)	All Randomized Patients with a baseline and at least one post-baseline observation while on IP	Last of Visits 1-4	Visits 7, 10, and 15 prior to discontinuation of IP
HbA1c categorical analysis longitudinal logistic regression	All Randomized Patients with a baseline and at least one post-baseline observation while on IP	Last of Visits 1-4	Visits 7, 10, and 15 prior to discontinuation of IP

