5.12.7.1. Treatment Emergent Anti-Insulin Lispro Antibody

The treatment-emergent anti-insulin lispro antibody (denoted as treatment-emergent antidrug antibody [TEADA] throughout this SAP) is based on the change from baseline (Visit 1) to post-baseline (post-Visit 1) in the anti-insulin lispro antibody level (percent binding). Treatment-emergent antidrug antibody can be subclassified as either treatment induced (not detected anti-insulin lispro antibody at baseline) or treatment boosted (detected anti-insulin antibody at baseline):

- treatment-induced response: change from not detected anti-insulin lispro at baseline (Visit 1) to postbaseline detected anti-insulin lispro
- treatment-boosted response: change from detected anti-insulin lispro at baseline (Visit 1) to postbaseline detected anti-insulin lispro antibody level (percent binding) at least 157% of the baseline value

The TEADA status will be determined using all data regardless of IP use. The number and percentage of patients with positive TEADA response any time during the treatment period will be summarized by treatment group. For patients with positive TEADA response any time during the treatment period, the number and percentage of patients with positive insulin cross-reactivity anytime during the treatment period, and the number and percentage of patients not meeting the TEADA criteria at Visit 15 (or last visit for patients who discontinue the study prior to Visit 15) will also be summarized by treatment group. Treatment groups will be compared by Fisher's exact test.

Both actual and change from baseline for the anti-insulin lispro antibody level in percent binding regardless of IP use will be summarized by scheduled visit prespecified in the protocol for patients with positive TEADA response anytime during the treatment period. The repeated measurement from Visit 1 to Visit 15 will be analyzed by an MMRM model with treatment, baseline value of the response variable, visit, and visit by treatment interaction as fixed factors and patient as the random factor. The ANCOVA model using treatment and baseline value as covariates will be used for the analysis of last nonmissing observation prior to or at Visit 15 and the analysis of maximum percent binding during the treatment period.

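### The SAP sets the anti-insulin lispro antibody baseline at Visit 1 in its immunogenicity sections and at Visit 4 in Table ITSB.5.2, and the antibody MMRM, read literally, uses the Visit 1 value as both outcome and covariate

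*SAP*

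**What the plan says.** **Immunogenicity text.** SAP 5.12.7 notes that sampling starts before the first lead-in dose of open-label Humalog and concludes: "Therefore, the blood sample result at Visit 1 will be considered as the anti-insulin lispro level at baseline for this study". SAP 5.12.7.1 makes TEADA "based on the change from baseline (Visit 1) to post-baseline (post-Visit 1) in the anti-insulin lispro antibody level" and repeats Visit 1 in both subclasses: induced (not detected at baseline, detected later) and boosted (later binding at least 157% of the baseline value).

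**Baseline table.** SAP 5.1 introduces Table ITSB.5.2 with the statement that it "shows the definition of baseline and post-baseline for each variable to be analyzed". Its antibody row gives Visit 4 as baseline and "Visits 7, 10, 15 regardless of IP use" as post-baseline.

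**Protocol.** Section 10.3.1 sets a default baseline, the last non-missing value at or before Visit 4, and allows exceptions. Section 10.3.6 defines TEADA without naming a visit. The Schedule of Activities places antibody samples at Visits 1, 4, 7, 10 and 15 and at early discontinuation.

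**Antibody MMRM.** SAP 5.12.7.1: "The repeated measurement from Visit 1 to Visit 15 will be analyzed by an MMRM model". The listed terms include the baseline value of the response. For vital signs, SAP 5.12.6 says instead: "The measurements during the treatment period (0 to 26 weeks) will be analyzed by an MMRM model".

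**The concern.** TEADA status is defined relative to baseline, so moving the baseline visit moves the denominator of the boosted rule and the starting status of the induced rule. Two programmers following different parts of the same SAP would produce different TEADA flags from the same data. Those flags feed the Fisher comparison of arms. They also define the subgroups in 5.12.7.1 for HbA1c, insulin dose, injection-site and hypersensitivity reactions, and documented hypoglycemia.

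Both versions can be rebuilt from the by-visit antibody listing, so no data are lost. The risk is that the version is chosen after treatment codes are known.

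The MMRM wording raises a second question. If the baseline is Visit 1 and the outcomes start at Visit 1, the same number stands on both sides of the model.

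**Working it through.** The plan gives no antibody rate, variance or power figure, so there is nothing of its own to reproduce.

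**1. The definitions side by side**

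| Source | Baseline | Post-baseline |
|---|---|---|
| SAP 5.12.7 | Visit 1 | not stated |
| SAP 5.12.7.1 | Visit 1 | after Visit 1 |
| SAP Table ITSB.5.2 | Visit 4 | Visits 7, 10, 15 |
| Protocol 10.3.1 (default) | last value at or before Visit 4 | not stated |

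The window after Visit 1 takes in Visit 4. However, 5.12.7.1 limits the TEADA incidence summary, and the analyses by TEADA status, to the treatment period ("For patients with positive TEADA response any time during the treatment period" is one instance). That narrows the window conflict. It does not close it fully, because the Schedule of Activities prints Visit 4 under the treatment-period heading. It says nothing about which visit is the denominator.

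**2. Effect on one patient (hypothetical values, % binding)**

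| Visit 1 / Visit 4 / later | Later ÷ Visit 1 | Later ÷ Visit 4 |
|---|---|---|
| 4.0 / 6.5 / 6.5 | 6.5/4.0 = 162.5%, positive | 6.5/6.5 = 100%, negative |
| 10.0 / 5.0 / 8.0 | 8.0/10.0 = 80%, negative | 8.0/5.0 = 160%, positive |

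The threshold is 157%. Status can move either way.

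**3. How many patients: illustration only.** Assume all patients have detected antibody at baseline, log binding varies independently between visits around a patient level, and a patient is boosted if the largest of Visits 7, 10 and 15 exceeds baseline by at least ln 1.57 = 0.451. For an assumed within-patient log SD of 0.10, 0.15 or 0.20 and no lead-in trend, simulation gives 0.4%, 7.1% or 18.2% of patients changing status, half each way, with incidence equal under the two baselines. At SD 0.15, an assumed lasting lead-in shift of −0.1 or +0.1 gives incidence of 1.3% or 11.6% (Visit 1) against 4.3% (Visit 4). The spread comes from the assumptions. The documents supply none of these inputs, and the induced category is not modelled.

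**4. The MMRM taken literally, Visit 1 as outcome and covariate.** Assume complete data, large samples, unit variance and a constant within-patient correlation r. There are five outcome visits (1, 4, 7, 10, 15). Variances are per (1/n₁ + 1/n₀).

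*Random intercept, equal residual variance.* The common slope settles at b = (1+4r)/5 instead of r.

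- Variance the model reports at Visit 15: b(1−b) + 0.8(1−r).
- True variance of that estimate: (1−r²) + (b−r)².
- Type I error: 2[1 − Φ(1.96 × SE ratio)].

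At r = 0.5, b = 0.6. The model variance is 0.24 + 0.40 = 0.64 and the true variance is 0.75 + 0.01 = 0.76. The SE ratio is √(0.64/0.76) = 0.918.

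| r | Model variance | True variance | SE ratio | Type I error |
|---|---|---|---|---|
| 0.3 | 0.8064 | 0.9296 | 0.931 | 6.8% |
| 0.5 | 0.6400 | 0.7600 | 0.918 | 7.2% |
| 0.7 | 0.4224 | 0.5136 | 0.907 | 7.5% |
| 0.85 | 0.2256 | 0.2784 | 0.900 | 7.8% |

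Once Visit 1 is not an outcome, b = r, both variances equal 1−r², and the type I error is 5.0%.

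*Unstructured covariance.* The Visit 1 residual is (1−b) times the Visit 1 value, and the later residuals given Visit 1 do not depend on b. The profile log-likelihood therefore contains −n·ln|1−b|, which grows without bound as b approaches 1. With n = 100 that term is 69 at b = 0.5, 461 at 0.99 and 1151 at 0.99999. The model has no proper maximum.

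**The case against.** **The immunogenicity section is the specific one and should prevail.** It gives a reason for Visit 1, and the protocol default permits exceptions. But the table's antibody row is equally specific, was added in SAP Version 2, and agrees with the protocol default. The SAP has no precedence rule. Each reading has textual support, so the objection does not settle the matter.

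**The protocol is contradicted.** A reader might infer this from the Visit 1 rule. The documents do not support it: the default is open to exceptions and 5.12.7 states one. What can be said is that Visit 1 departs from the default and Visit 4 does not.

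**The MMRM phrase only describes the sampling span.** This is plausible. The vital-signs model in 5.12.6 takes treatment-period measurements only, and the analysis of maximum binding in 5.12.7.1 is limited in the same way. The MMRM point is therefore a wording query with a consequence if followed literally, not proof that a faulty model will be run.

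**Standard errors will be too small.** A reader might infer this as a general result from the table in step 4. It holds only for a random intercept with equal residual variance. SAP 5.12.7.1 calls patient a random factor and names no covariance structure, while protocol 10.3.1 makes unstructured covariance the general choice for MMRM. There the model is degenerate. Its limit as b approaches 1 is a change-score analysis, with type I error simulated at 4.8% to 5.0% and a standard error √(2/(1+r)) times that of baseline-adjusted ANCOVA, which is 4% larger at r = 0.85 and 24% larger at r = 0.3. Misspecification stands under both structures; inflated error stands under one.

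**A known share of patients is misclassified, or one arm is favoured.** Nothing in the documents supports a count or a direction.

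**Conclusion.** The SAP as written contains two incompatible antibody baselines, and TEADA status depends on which is followed. This rests on the text alone and on no assumption. The post-baseline windows also differ, but the treatment-period limits remove most of that difference. The number of patients affected and the net direction cannot be derived.

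The antibody MMRM, if run as worded with the Visit 1 baseline, is misspecified. Type I error at Visit 15 is about 6.8% to 7.8% under a random intercept with equal residual variance and an assumed correlation of 0.3 to 0.85; under unstructured covariance the model is degenerate. Loose wording is a fair alternative explanation.

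Severity is minor. Objective 12 is exploratory and carries no multiplicity adjustment (SAP 5.5), and the primary and gated HbA1c analyses do not use the antibody baseline.

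**What to change.** Before unblinding:

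1. State one antibody baseline visit and one post-baseline window in the same words in SAP 5.12.7, 5.12.7.1 and Table ITSB.5.2. Give the reason if the choice departs from the protocol default.
2. Either visit can be defended. Visit 1 precedes the lead-in Humalog, although protocol inclusion criterion [4] admits patients already on insulin lispro. Visit 4 isolates what follows randomization and fits the table's treatment-period TEAE row, where baseline is "Prior to first dose of randomized IP (or v4 date if missing), after first dose of open label Humalog". If Visit 1 is kept, say whether the Visit 4 sample counts as post-baseline.
3. Restrict the antibody MMRM outcomes to Visits 7, 10 and 15, so that the baseline value is never also an outcome, and name the covariance structure.

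The cost is SAP wording only, since both samples are already scheduled and listed by visit. A supplementary summary using the other baseline is optional.
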